PBMC Collection (for determination of FVIII and Capsid specific CTL activity)	X				Х			Х	
Von Willebrand Factor Antigen (VWF:Ag)	Х				2	X		Х	
PCR of vector DNA in blood, saliva, urine, semen, and stools ^e	Xe	Xe	Xe		Σ	Ke		Х	
Exploratory biomarker assessments ^g	Х				2	X		Х	
Haemo-QoL-A QoL assessment	Xf				Σ	ζf		Х	

Table 9.1.5: Schedule of Events – Safety Follow-Up (Years 2-5)

* Visit windows are ± 2 weeks for visits in Years 2-5. The Q6W visits during Years 3-5 should restart after each End of Year visit (eg, the first Q6W visit during Year 3 should be ~6 weeks after the End of Year 2 visit).

^a Complete physical examination should be performed at the End of Year visits; brief physical examination may be performed at other study visits. Weight should be recorded at the second Q12W visit each year and at every End of Year visit during Years 2-5.

Proprietary and Confidential

31 January 2019

^b Refer to Table 9.7.8.2.1 for laboratory assessments to be included, and to Table 9.7.8.3.1 for liver tests. LTs may be monitored more or less frequently (and in particular when ALT values are $\geq 1.5x$ ULN) based on discussion between the Medical Monitor and the Investigator and review of subject data, but LTs will be monitored at least twice weekly during periods when a subject's ALT is $\geq 3x$ ULN. Patients with ALT $\geq 1.5x$ ULN during the study may undergo additional evaluations (eg, imaging studies including MRI or ultrasound, additional blood tests, and/or liver biopsy) at the discretion of the investigator. Additional testing of FVIII and LTs during any study week may be performed if: (1) the ALT has increased to above ULN or increased by > 10 U/L from prior assessment; (2) Increases in ALT values from prior assessment are accompanied by declines in FVIII activity level; or after a discussion between the Medical Monitor and the Investigator based on a review of subject data. If FVIII levels and/or ALT values are stable over the course of several weeks, assessment of FVIII activity and ALT levels may be adjusted based on discussion between the Medical Monitor and the Investigator between the Medical Monitor and the Investigator. During Years 2-5 of the Post-Infusion Follow-Up period, urine tests and blood, chemistry, and coagulation tests should be performed at the second Q12W visit each year and at every End of Year visit.

- ^c Includes hFVIII activity level (one-stage clotting and chromogenic substrate assay). If a subject has used FVIII within 72 hours of a measurement day, all efforts should be made to obtain FVIII activity measurements when a 72 hour interval without FVIII use is achieved; the 72-hour wash-out period is only intended for subjects who have achieved FVIII \geq 5 IU/dL at 16 weeks after BMN 270 infusion and who have not resumed standard of care FVIII replacement therapy. If FVIII levels are elevated or stable over the course of several weeks, assessment of FVIII activity may be adjusted based on discussion between the Medical Monitor and the Investigator. A d-dimer may be considered under circumstances in which FVIII activity levels are above the normal physiological range and/or if there is a concern for a venous thromboembolism. If a subject tests positive in the Bethesda assay (with Nijmegen modification) during Years 3-5, a fresh sample should be collected within 4 weeks of the initial visit that had a positive result.
- ^d Includes hFVIII activity level (one-stage clotting and chromogenic substrate assay), Bethesda assay (with Nijmegen modification) for hFVIII inhibitor level, hFVIII coagulation activity exploratory assay, and hFVIII antigen (ELISA). If a subject has used FVIII within 72 hours of a measurement day, all efforts should be made to obtain FVIII activity measurements when a 72 hour interval without FVIII use is achieved; the 72-hour wash-out period is only intended for subjects who have achieved FVIII \geq 5 IU/dL at 16 weeks after BMN 270 infusion and who have not resumed standard of care FVIII replacement therapy. If FVIII levels are elevated or stable over the course of several weeks, assessment of FVIII activity may be adjusted based on discussion between the Medical Monitor and the Investigator. A d-dimer may be considered under circumstances in which FVIII activity levels are above the normal physiological range and/or if there is a concern for a venous thromboembolism. If a subject tests positive in the Bethesda assay (with Nijmegen modification) in years 3-5, a fresh sample should be collected within 4 weeks of the initial visit that had a positive result.
- ^e Sample testing during Safety Follow-Up is not required if at least 3 consecutive samples are cleared during the Post-Infusion Follow-Up period. Subjects who have not had 3 consecutive negative samples by Week 52 should continue to have PCR testing every 4 weeks (during Year 2) or every 6 weeks (during Years 3-5) until 3 consecutive negative samples are documented (or upon consultation between the Investigator and Medical Monitor).
- ^fHaemo-QoL-A QoL assessment during Years 2-5 of Safety Follow-up should be performed at the second Q12W visit each year and at every End of Year visit.
- ^g Blood samples will be collected to evaluate biochemical, molecular, cellular, and genetic/genomic aspects relevant to hemophilia A, coagulation, and/or AAV gene transfer, and to develop assays used for these evaluations. Subjects may choose to opt out of the exploratory genetic/genomic research being done to study or try to discover genes that are not yet known to be associated with hemophilia A. While exploratory samples will be collected at the time points indicated above, testing of these samples (including any other exploratory assessments) will be performed only as deemed necessary by the Sponsor.
- ^h Subjects who meet the definition of treatment failure to BMN 270 therapy after Week 52 may omit the Q4W and Q6W visits during Years 2-5, and must attend only the Q12W and End of Year visits. Such subjects following the abbreviated schedule who have not yet cleared vector shedding in all fluids must still provide samples Q4W (during Year 2) or Q6W (during Years 3-5) until vector shedding has been cleared (but do not need to do other scheduled assessments at those visit dates).

270-201 Amendment 8

					Steroid T	reatment	Period ^d					Post-Steroid Period ^c					
	Week 1	Week 2	Week 3	Week 4	Week 5	Week 6	Week 7	Week 8	Week 9	Week 10	Week 11 ^b	Week 1	Week 2	Week 3	Week 4	Week 13	
Therapeutic corticosteroids (dose in mg/day) ^a	60 mg	60 mg	40 mg	40 mg	30 mg	30 mg	20 mg	20 mg	15 mg	10 mg	5 mg						
FVIII activity testing												Х	Х	Х	Х		
Liver testing												Х	Х	Х	Х		
Hepatitis B testing ^e						Х						Х				Х	
HCV Viral Load ^e						Х						Х				Х	

Table 9.1.6: Schedule of Events – Therapeutic Corticosteroids for LT Elevations

^a Therapeutic corticosteroids may be initiated when a subject's ALT value is ≥ 1.5x ULN or based on review of FVIII and liver enzyme data after consultation between the Investigator and the Medical Monitor.

^b Following initiation or completion of steroid regimen, if ALT elevation ≥ 1.5x ULN is reported, steroid management decisions will based on discussions between the Investigator and Medical Monitor. Modification of the steroid regimen may take into consideration possible confounders for the ALT elevation and impact on FVIII expression.

^c After discontinuation of corticosteroids, weekly labs for ALT and FVIII levels will be measured once a week for 4 weeks to ensure stability in values. If these assessments are already being done as part of normal study follow-up, they do not need to be duplicated.

^d Regardless of the assessments listed in the Schedule of Assessments (Table 9.1.2, Table 9.1.3, or Table 9.1.4), subjects initiated on corticosteroids will only be required to have laboratory evaluations on a weekly basis.

^e Should only be performed in subjects with a history of hepatitis B or hepatitis C prior to study entry.

270-201 Amendment 8

	Within 28 Days Before Biopsy Day	Within 7 Days Before Biopsy Day	1 Day Before Biopsy Day ^d	Biopsy Day (BD)
Informed Consent	Х			
Liver Ultrasound ^a	X			
Brief Physical Examination	X		X	Х
Hematology, Coagulation, Chemistry Assessments ^b	X		X	
Liver Tests ^b	X		X	Х
FibroScan		Х		
Local FVIII Activity Level Assessment		Х	X	Х
Pre-Biopsy Consultation ^c		Х		
Liver Biopsy ^e				Х

Table 9.1.7: Schedule of Events – Liver Biopsy Substudy

^a Liver ultrasound must be performed within 28 days prior to the scheduled biopsy, unless an ultrasound result from the prior 3 months is already available.

^b Refer to Table 9.7.8.2.1 for laboratory assessments to be included, and to Table 9.7.8.3.1 for liver tests.

^c Subjects will undergo a pre-biopsy consultation with the investigator (treating hematologist).

^d Subjects may need to repeat/extend this visit if their FVIII activity levels need adjustment before the biopsy, at the discretion of the investigator (treating hematologist).

^e Biopsy will be a percutaneous or transjugular biopsy under ultrasound guidance, performed according to the standard procedure of the institution. If only a small amount of tissue (< 2 cm) is obtained at the time of the biopsy, the subject may be asked to consent for a second pass. In this case, the original < 2 cm sample should still be retained and handled according to the instructions for handling biopsy specimens in the Laboratory Manual. Following completion of the biopsy, the subject should remain in the hospital under observation for at least 4-6 hours. Overnight post-procedure observation may be done at the investigator's discretion.

270-201 Amendment 8

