- ^d Includes hFVIII activity level (one-stage clotting assay and chromogenic substrate assay), Bethesda assay (with Nijmegen modification) for hFVIII inhibitor level, hFVIII coagulation activity exploratory assay, and hFVIII antigen (ELISA). If a subject has used FVIII within 72 hours of a measurement day, all efforts should be made to obtain FVIII activity measurements when a 72-hour interval without FVIII use is achieved; the 72-hour wash-out period is only intended for subjects who have achieved FVIII \geq 5 IU/dL at 16 weeks after BMN 270 infusion and who have not resumed standard of care FVIII replacement therapy. If FVIII levels are elevated or stable over the course of several weeks, assessment of FVIII activity may be adjusted based on discussion between the Medical Monitor and the Investigator. A d-dimer may be considered under circumstances in which FVIII activity levels are above the normal physiological range and/or if there is a concern for a venous thromboembolism.
- ^e Collection to occur on Day 2 and 4 following BMN 270 infusion, and then until at least 3 consecutive negative results are obtained. Collection and testing of semen samples must continue through Week 12, even if 3 consecutive negative samples in that compartment have already been recorded.

^f Blood samples will be collected to evaluate biochemical, molecular, cellular, and genetic/genomic aspects relevant to hemophilia A, coagulation, and/or AAV gene transfer, and to develop assays used for these evaluations. Subjects may choose to opt out of the exploratory genetic/genomic research being done to study or try to discover genes that are not yet known to be associated with hemophilia A. While exploratory samples will be collected at the time points indicated above, testing of these samples (including those for Direct Thrombin Activity test and any other exploratory assessments) will be performed only as deemed necessary by the Sponsor.

^g Testing for reactivation of hepatitis B and hepatitis C at Week 16, for subjects with a past medical history of Hepatitis B or Hepatitis C prior to study entry, should be performed only in subjects who have not received therapeutic corticosteroids prior to Week 16; subjects who have received therapeutic corticosteroids will have hepatitis B and hepatitis C testing at the time points indicated in Table 9.1.6.

270-201 Amendment 8

	Follow-Up After BMN 270 Administration – Weeks*															

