
- ^c Includes hFVIII activity level (one-stage clotting and chromogenic substrate assay). If a subject has used FVIII within 72 hours of a measurement day, all efforts should be made to obtain FVIII activity measurements when a 72-hour interval without FVIII use is achieved; the 72-hour wash-out period is only intended for subjects who have achieved FVIII \geq 5 IU/dL at 16 weeks after BMN 270 infusion and who have not resumed standard of care FVIII replacement therapy. If FVIII levels are elevated or stable over the course of several weeks, assessment of FVIII activity may be adjusted based on discussion between the Medical Monitor and the Investigator. A d-dimer may be considered under circumstances in which FVIII activity levels are above the normal physiological range and/or if there is a concern for a venous thromboembolism.
- ^d Includes hFVIII activity level (one-stage clotting and chromogenic substrate assay), Bethesda assay (with Nijmegen modification) for hFVIII inhibitor level, hFVIII coagulation activity exploratory assay, and hFVIII antigen (ELISA). If a subject has used FVIII within 72 hours of a measurement day, all efforts should be made to obtain FVIII activity measurements when a 72-hour interval without FVIII use is achieved; the 72-hour wash-out period is only intended for subjects who have achieved FVIII \geq 5 IU/dL at 16 weeks after BMN 270 infusion and who have not resumed standard of care FVIII replacement therapy. If FVIII levels are elevated or stable over the course of several weeks, assessment of FVIII activity may be adjusted based on discussion between the Medical Monitor and the Investigator. A d-dimer may be considered under circumstances in which FVIII activity levels are above the normal physiological range and/or if there is a concern for a venous thromboembolism.

^e Collection for each matrix to occur until at least 3 consecutive negative results are obtained.

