- ^d Includes hFVIII activity level (one-stage clotting and chromogenic substrate assay), Bethesda assay (with Nijmegen modification) for hFVIII inhibitor level, hFVIII coagulation activity exploratory assay, and hFVIII antigen (ELISA). If a subject has used FVIII within 72 hours of a measurement day, all efforts should be made to obtain FVIII activity measurements when a 72 hour interval without FVIII use is achieved; the 72-hour wash-out period is only intended for subjects who have achieved FVIII \geq 5 IU/dL at 16 weeks after BMN 270 infusion and who have not resumed standard of care FVIII replacement therapy. If FVIII levels are elevated or stable over the course of several weeks, assessment of FVIII activity may be adjusted based on discussion between the Medical Monitor and the Investigator. A d-dimer may be considered under circumstances in which FVIII activity levels are above the normal physiological range and/or if there is a concern for a venous thromboembolism.

^e Sample testing during Safety Follow-Up is not required if at least 3 consecutive samples are cleared during the Post-Infusion Follow-Up period.

^f Blood samples will be collected to evaluate biochemical, molecular, cellular, and genetic/genomic aspects relevant to hemophilia A, coagulation, and/or AAV gene transfer, and to develop assays used for these evaluations. Subjects may choose to opt out of the exploratory genetic/genomic research being done to study or try to discover genes that are not yet known to be associated with hemophilia A. While exploratory samples will be collected at the time points indicated above, testing of these samples (including those for Direct Thrombin Activity test and any other exploratory assessments) will be performed only as deemed necessary by the Sponsor.

270-201 Amendment 8

	Years 2-5*	Year 2*	Years 3-5*						
	01000	O ATT	O(Wh	Year 2	Year 3	Year 4	Year 5	ETV	
Assessment	Q12W	Q4W ^h	Q6W ^h	W104	W156	W208	W260		
Physical examination ^a	Xa				Xa				
Weight ^a	Xa				У	K ^a		Х	
Assessment of Adverse Events and Concomitant Medications (including review of subject diary for bleeding and FVIII use)	X	Х	X		Х				
Vital Signs	Х			Х				Х	
Blood chemistry, haematology, coagulation screen, and CRP ^b	Х			Х				Х	
Urine Tests ^b	Х			Х				Х	
Liver Tests (local) ^b	Х	Х	Х	Х				Х	
FVIII assays (local) ^c	Х	Х	Х	Х				Х	
Liver Tests (central) ^b	Х	Х	X	Х				Х	
FVIII assays (central) ^d	Х	Х	Х		2	X		Х	
AAV5 antibody titer	Х				2	X		Х	
FVIII antibody titer	Х				Х			Х	

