9.3.1 Inclusion Criteria

Individuals eligible to participate in this study must meet all of the following criteria:

- 1. Males that are 18 years or older with established severe Haemophilia A as evidenced by their medical history. Patients will be considered as severe if their base FVIII level is 1 IU/dL or less
- 2. Treated/exposed to FVIII concentrates or cryoprecipitate for a minimum of 150 exposure days (EDs)
- 3. Greater or equal to 12 bleeding episodes only if on on-demand therapy over the previous 12 months. Does not apply to patients on prophylaxis
- 4. Able to sign informed consent and comply with requirements of the trial
- 5. No history of inhibitor, and results from a modified Nijmegen Bethesda assay of less than 0.6 Bethesda Units (BU) 2 consecutive occasions at least one week apart within the past 12 months
- 6. Sexually active patients must be willing to use an acceptable method of contraception such as double barrier, including hormonal contraception for at least 6 months post-treatment. After 6 months, subjects may stop contraception use only if they have had 3 consecutive negative semen samples.

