9.6 Dietary or Other Protocol Restrictions

There are no dietary or other protocol restrictions for this study.

Subjects should be advised to abstain from any blood or sperm donation after BMN 270 infusion, until there is no further evidence of vector shedding from PCR analysis of samples.

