9.7.8.6 Vector Shedding

Vector shedding has been extensively studied in all similar clinical trials performed to date. (Nathwani, 2014, N.Engl.J.Med.); (Manno, 2006, Nat.Med.); (Schenk-Braat, 2007, J.Gene Med.); (Croteau, 2004, Ann.Occup.Hyg.). In the literature referenced above, including Haemophilia B clinical studies utilizing AAV2 and AAV8, vector was no longer detectable after 40 days in blood, saliva, urine or stool, but in one study was detected in the seminal fluid but not in motile sperm (Manno, 2006, Nat.Med.). In these studies, the amount of vector present in these bodily fluids involved an extremely small fraction of the infused dose. More recent data from an ongoing AAV-FIX study demonstrates persistence of the vector in both the blood and the semen for at least 39 weeks (Miesbach, 2016, Haemophilia).

During the Post-Infusion Follow-Up period, subjects will undergo testing of various bodily samples to look for evidence of vector shedding for possible viral transmission. Bodily

fluids will be tested by PCR at the time points indicated in Table 9.1.2, Table 9.1.3, Table 9.1.4, and Table 9.1.5. Fluids tested will include:

- Blood
- Saliva
- Semen
- Urine
- Stool

Vector shedding will also be extensively studied in the present clinical trial, every other week between Weeks 4-16, then every 4 weeks to Week 52 until at least 3 consecutive negative results are obtained. Testing of semen will continue through Week 12, even if 3 consecutive negative results have been recorded in that compartment prior to that timepoint. Subjects who have not had 3 consecutive negative samples by Week 52 should continue to have PCR testing every 4 weeks until 3 consecutive negative samples are documented (or upon consultation between the Investigator and Medical Monitor). Subjects who meet the definition of treatment failure and wish to follow an abbreviated schedule (refer to Section 12.5.3 but who have not cleared vector shedding from all fluids must still provide samples for assessment until vector shedding has cleared: every 4 weeks (during Year 2), or every 6 weeks (during Years 3-5).

Contraception use may need to be extended beyond 26 weeks in individual subjects based on observed vector shedding in semen. After 6 months, subjects may stop contraception use only if they have had 3 consecutive negative semen samples (upon consultation between the Investigator and Medical Monitor).

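### A semen PCR positive at Week 10 or 12 that follows three consecutive negatives triggers no required further semen PCR, because the stopping rule and the later waivers are already met by the earlier run

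*Protocol*

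**What the plan says.** All references are to the Amendment 8 text of the Protocol.

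- **Semen minimum.** Table 9.1.2, footnote e: "Collection and testing of semen samples must continue through Week 12, even if 3 consecutive negative samples in that compartment have already been recorded". Section 9.7.8.6 repeats it: "Testing of semen will continue through Week 12, even if 3 consecutive negative results have been recorded in that compartment prior to that timepoint". Section 12.5.4 agrees.
- **Stopping rule.** Table 9.1.2, footnote e: "Collection to occur on Day 2 and 4 following BMN 270 infusion, and then until at least 3 consecutive negative results are obtained". Table 9.1.3, footnote e, for Weeks 17-32: "Collection for each matrix to occur until at least 3 consecutive negative results are obtained".
- **Waivers.** Table 9.1.4, footnote e: "Sample testing during Safety Follow-Up is not required if at least 3 consecutive samples are cleared during the Post-Infusion Follow-Up period". Table 9.1.5 (footnote e) and Sections 12.6.4, 12.7.2, 12.8.1 to 12.8.3 and 12.10 waive testing on the same kind of condition. After Week 52, semen PCR is asked only of subjects who have not had three consecutive negatives.
- **Contraception.** Inclusion criterion 6 requires at least 6 months and then says: "After 6 months, subjects may stop contraception use only if they have had 3 consecutive negative semen samples". Section 9.7.8.6 adds a consultation: "subjects may stop contraception use only if they have had 3 consecutive negative semen samples (upon consultation between the Investigator and Medical Monitor". It also says that use may need to run beyond 26 weeks where shedding in semen is observed.
- **Donation.** Section 9.6 advises against blood or sperm donation "until there is no further evidence of vector shedding from PCR analysis of samples".

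**The concern.** Semen is the only matrix in which sampling must go on after three negatives. In blood, saliva, urine and stool the run normally ends collection, so no later result normally exists to contradict it. In semen the extra samples have safety value only if a positive among them has a consequence, and none is stated. Each rule asks whether a run of three negatives exists. None asks whether it is the latest evidence.

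Section 9.7.8.6 says that shedding is tested because of possible viral transmission. Under the rules as written, required semen PCR can end with a positive as the latest result. The contraception decision after 6 months and the donation advice both depend on PCR evidence, and they might then rest on no newer semen result. The halt criterion in Section 9.3.4.1 on vector in semen beyond 52 weeks also could not be assessed for such a subject without further testing.

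**Working it through.** This is a question of rule logic, and the plan gives no figure to reproduce.

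**Inputs.** PCR time points in Table 9.1.2: Days 2, 4 and 8, then Weeks 4, 6, 8, 10, 12, 14 and 16. Tables 9.1.3 and 9.1.4: Weeks 20, 24, 28, 32, 36, 40, 44, 48 and 52. Section 9.3.6 gives the Post-Infusion Follow-Up period as 16 weeks, so a run at Weeks 4, 6 and 8 falls inside it.

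**Example: negative at Weeks 4, 6 and 8, positive at Week 12.**

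| Rule | Met by the Week 4-6-8 run? | Changed by the Week 12 positive? |
|---|---|---|
| Stopping rule (Tables 9.1.2 and 9.1.3, Sections 9.7.8.6 and 12.5.4) | Yes, at Week 8 | No |
| Semen minimum to Week 12 | Satisfied at Week 12 | No |
| Safety Follow-Up and early-termination waivers (Table 9.1.4, Sections 12.6.4, 12.7.2, 12.10) | Yes | No |
| Years 2-5 waivers (Table 9.1.5, Sections 12.8.1 to 12.8.3) | Yes | No |
| Three-negative condition for contraception (criterion 6, Section 9.7.8.6) | Yes | Not the condition itself; consultation and possible extension apply |

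**Time points no longer required for semen.** Before Week 26: Weeks 14, 16, 20 and 24, which is 4. From Week 28 to Week 52: Weeks 28, 32, 36, 40, 44, 48 and 52, which is 7. Total 4 + 7 = 11. From the Week 12 positive to Week 26 is 26 - 12 = 14 weeks, all inside the mandatory 6 months of contraception.

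**If the three negatives had to follow the last positive.**
- Positive at Week 12: negatives at Weeks 14, 16 and 20, so clearance at Week 20 at the earliest, with 3 samples after Week 12.
- Positive at Week 10, negative at Week 12: negatives at Weeks 12, 14 and 16, so clearance at Week 16 at the earliest, with 2 samples after Week 12.

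**How many result patterns reach the gap.** Five runs can be complete before Week 12: Days 2-4-8; Days 4-8 and Week 4; Day 8 and Weeks 4-6; Weeks 4-6-8; Weeks 6-8-10. The 8 visits from Day 2 to Week 12 give 2^8 = 256 positive/negative patterns. The stopping rule is met by Week 12 in 107. Of these, 67 have a positive at Week 10 and/or Week 12 after the run. Counting only results from Day 8 on, the figures are 80 and 44. These are counts of logical patterns, not probabilities. They show only that the gap is not confined to one contrived sequence.

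**The case against.** Several counter-arguments have force.

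- **Contraception release is not automatic.** A reader might infer that the old run by itself frees the subject. It does not. The run is a necessary condition, Section 9.7.8.6 adds consultation between the Investigator and the Medical Monitor, and a Week 10 or 12 positive is the kind of observed shedding for which it allows extension. This stands.
- **The 14 weeks to Week 26 are not unprotected.** Inclusion criterion 6 requires contraception for at least 6 months whatever the PCR results. This stands.
- **The rules set minimums.** Nothing bars a further sample, and the donation advice is hard to lift after a positive without one. So later decisions might rest on no newer semen result; the text does not show that they would. This stands too.
- **Clearance may be what was meant.** Subjects on the abbreviated schedule must give samples until shedding has cleared, and a site could sensibly read the rule as the latest three results. However, that wording applies only to treatment failures, it does not define clearance, and a site that follows the literal rule commits no deviation.
- **The 39-week citation does not show this pattern.** Section 9.7.8.6 reports persistence of vector in blood and semen in another AAV study. A persistently positive subject never obtains three negatives and stays in testing. No section shown reports negatives followed by a positive.
- **The practical effect is small and partly past.** Section 14.7 allows up to 15 subjects, and the Amendment 7 rationale says that all had already gone through Screening.

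These points limit the harm. None of them makes a further semen PCR required.

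**Conclusion.** The concern holds in a limited form and should be corrected. Followed exactly, the Protocol lets required semen PCR end on a positive at Week 10 or 12. This is a wrong outcome of a stated rule, not a detail left to another document. None of the 11 later time points in Year 1 is required for semen in such a subject, and the Years 2-5 and early-termination waivers apply as well.

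The consequence lies in contraception decisions after 6 months, the donation advice and follow-up testing through Years 2-5. The documents do not support reading this as automatic release from contraception, as an unprotected interval before Week 26, or as a fault in the other matrices. The efficacy analysis is unaffected. The frequency is unknown, and at most 15 subjects are concerned. Because all had been screened by Amendment 7, much of the Year 1 schedule may already be past, and an enrolment halt under Section 9.3.4.1 would now have limited effect.

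The conclusion assumes that no part of the Protocol outside the text shown resets the count.

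**What to change.** Add to Section 9.7.8.6, and cross-refer from footnote e of Tables 9.1.2 to 9.1.5, Sections 12.5.4, 12.6.4, 12.7.2, 12.8.1 to 12.8.3 and 12.10, and inclusion criterion 6:

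*For semen, the 3 consecutive negatives must be the most recent results, with the last collected at or after Week 12. A later positive restarts the count, and semen PCR continues at the scheduled PCR visits (Q4W in Year 2, Q6W in Years 3-5) until 3 consecutive negatives follow it. Contraception may stop after 6 months only when this is met.*

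The existing consultation between the Investigator and the Medical Monitor stays. The other matrices need no change.

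Check the existing semen PCR records once, for at most 15 subjects. Resume semen PCR at scheduled visits for any subject whose last run of three negatives preceded a positive.

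The cost is one amendment of wording and that single check. An affected subject gives at least 2 further samples (positive at Week 10, negative at Week 12) or at least 3 (positive at Week 12), and more if another positive appears. Contraception, and the reported duration of shedding, may be longer for that subject.
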